4.2 Exclusion Criteria

Any of the following would exclude the subject from participation in the study:

1. Contrast-enhancing tumor in brainstem or spinal cord (subjects do not need spinal MRI for screening, but known spinal cord tumor is exclusionary)
2. Diffuse leptomeningeal disease
3. Prior bevacizumab or other vascular endothelial growth factor (VEGF/VEGFR) inhibitors (exception: prior bevacizumab is allowed if it was administered for the treatment of radiation necrosis rather than progressive tumor and was stopped at least 4 weeks prior to MRI showing demonstrating tumor progression).
4. Patients with clinically significant mass effect or midline shift (e.g., 1-2 cm of midline shift)
5. Use of any immunosuppressive medication other than steroids, including but not limited to antimetabolites, calcineurin inhibitors, and/or anti-TNF agents within six months of start of study drug
6. Prior diagnosis of immunodeficiency
7. Prior solid organ or bone marrow transplantation
8. Autoimmune or connective tissue disease that is EITHER (a) actively flaring OR (b) has required systemic treatment in the past 2 years (i.e., with use of disease modifying agents, corticosteroids, or immunosuppressive drugs).
EXCEPTIONS: Subjects with type I diabetes mellitus, hypothyroidism only requiring hormone replacement, adrenal insufficiency requiring only replacement dose corticosteroids, skin disorders (such as vitiligo, psoriasis, pemphigus, or alopecia) controlled with topical medications, or conditions not expected to recur in the absence of an external trigger are permitted to enroll. Patients with asthma that is not actively flaring are allowed. Patients with history of Grave's disease that is previously treated with thyroidectomy or radioiodine are allowed. Patients with celiac disease whose symptoms are controlled with a gluten-free diet are allowed. Patients with rheumatoid arthritis and other arthropathies such as ankylosing

spondylitis, Sjogren's syndrome, Raynaud syndrome, and patients with positive serologies, such as antinuclear antibodies (ANA) or anti-thyroid antibodies, should be evaluated for the presence of target organ involvement and potential need for systemic treatment but should otherwise be eligible.

9. History of non-infectious pneumonitis that required steroid treatment

10. Known active hepatitis B virus (HBsAg reactive) or active hepatitis C virus (HCV RNA detectable by PCR)

11. Human immunodeficiency virus (HIV)-positive patients on antiretroviral therapy

12. Patients with a prior or concurrent malignancy whose natural history or treatment has the potential to interfere with the safety or efficacy assessment of the investigational regimen are excluded from this trial. Otherwise, patients with prior or concurrent malignancy are eligible.

13. Any serious, uncontrolled medical disorder, nonmalignant systemic disease, or active, uncontrolled infection that, in the opinion of the investigator, would put the subject at undue risk from the study treatment.

14. Patients with uncontrolled or significant cardiovascular disease including, but not limited to, any of the following are ineligible:

- Myocardial infarction or uncontrolled angina within 90 days prior to consent
- History of clinically significant arrhythmia (such as ventricular tachycardia, ventricular fibrillation, or torsades pointes)
- History of cardiomyopathy, pericarditis, significant pericardial effusion, myocarditis, or New York Heart Association (NYHA) functional class III-IV congestive heart failure

15. Known hypersensitivity to another monoclonal antibody that cannot be controlled with standard measures (e.g., antihistamines and corticosteroids)

16. Prisoners or subjects who are involuntarily incarcerated

17. Subjects who are compulsorily detained for treatment of either a psychiatric or physical (eg, infectious disease) illness

18. Pregnant women are excluded

19. Received a live vaccine within 30 days prior to first dose of study drug. Examples include but are not limited to measles, mumps, rubella, varicella/zoster, yellow fever, rabies, Bacillus Calmette-Guerin (BCG), and typhoid. Intranasal influenza vaccines are not allowed.

20. Participant must not be simultaneously enrolled in any interventional clinical trial

5 STUDY INTERVENTION

5.1 Description of Study Drugs

5.1.1. INCMGA00012

INCMGA00012 (also known as MGA012) is a humanized, hinge-stabilized, IgG4 κ mAb that recognizes human PD-1. INCMGA00012 contains a human IgG4 Fc domain to limit effector function while retaining neonatal FcRn binding to extend circulating t $\frac{1}{2}$. INCMGA00012 is designed to target PD-1-expressing cells, including T cells, and sustain/restore their effector function by blocking checkpoint inhibitory interactions between PD-1 and its 2 ligands, PD-L1 and PD-L2. INCMGA00012 is derived from a murine mAb clone that was generated using standard hybridoma technology from mice immunized with a His-tagged, human PD-1 extracellular domain molecule. INCMGA00012 drug product is formulated at a concentration of 25 mg/mL in sodium acetate trihydrate, acetic acid, sucrose, and polysorbate 80 at pH 5.1.

Complete physical, chemical, and pharmaceutical properties and formulations for INCMGA00012 are available in the Investigator's Brochure.

5.1.2. INCAGN01876

INCAGN01876 (previously designated as AGEN1876) is a recombinant, humanized immunoglobulin G1 (IgG1) kappa (κ) mAb that binds to the extracellular domain of the human tumor necrosis factor receptor superfamily member 18 (TNFRSF18), also known as glucocorticoid-induced TNFR-related protein (GITR). INCAGN01876 drug product is formulated at a concentration of 10 mg/mL in histidine, sucrose, and polysorbate 80 at pH 6.0.

Complete physical, chemical, and pharmaceutical properties and formulations for INCAGN01876 are available in the Investigator's Brochure.

5.2 Receipt of Investigational Agents

The investigational agents will be shipped from Incyte Corporation to:
Penn Investigational Drug Service Central
[name]
[name]
[contact] (phone)
[contact] (fax)

Receipt and product verification will be overseen by the Penn Investigational Drug Service (IDS). Shipments of study drugs will be arranged by Penn IDS on an as-needed basis. Certificates of delivery should be signed by Penn IDS.

5.3 Storage of study products

5.3.1. INCMGA00012

INCMGA00012 drug product should be stored under refrigeration at 2°C to 8°C.

5.3.2. INCAGN01876

INCAGN01876 drug product should be stored under refrigeration at 2°C to 8°C.

5.4 Study drug Accountability

Dispensation of study drugs from IDS should be recorded in the appropriate sections of the eCRF. IDS will only dispense study drugs to study subjects for whom the PI or delegated team member has signed an order. The study drugs provided for this study will be used only as directed in the study protocol.

The Investigator or designee is responsible for maintaining accurate dispensing records of the study treatments throughout the clinical study. The study treatment accountability log includes information including a patient identifier, amount and date dispensed, and amount and date returned to the pharmacy. Product returned to the pharmacy will be stored under the same conditions as products not yet dispensed but will be marked as 'returned' and kept separate from the products not yet dispensed.

5.5 Study drug Administration

5.5.1 Administration of INCMGA00012

INCMGA00012 is administered as an IV infusion over 60 minutes for the first infusion. If well tolerated, it may be administered over 30 minutes for subsequent treatments. On days when both study drugs are due to be administered, INCMGA00012 study product is administered first prior to administration of INCAGN01876. The only dose of INCMGA00012 used for this study is 500mg. There is no dose escalation or reduction. A 1-hour observation period is recommended after the INCMGA00012 infusion prior to beginning the INCAGN01876 infusion.

Infusion-related reactions (including anaphylaxis or cytokine release syndrome) may be associated with the administration of therapeutic antibodies. Of 199 prior study participants who have received infusions of INCMGA00012 in Study INCMGA 0012-101, 5 participants have experienced 1 infusion-related reaction each (see IB). This does not exceed the expected incidence of IRRs for the PD-1 inhibitor class. Infusion-related reactions were observed in Study INCMGA 0012-101 regardless of whether prophylaxis was administered; therefore, routine prophylaxis is not recommended. Secondary prophylaxis is recommended for participants who have experienced IRRs to INCMGA00012. Participants who experience life-threatening infusion reactions should not be retreated with INCMGA00012. Infusions reactions should be managed according to the guidelines in [Section 5.8.2](#).

5.5.2 Administration of INCAGN01876

INCAGN01876 is administered as an IV infusion over 60 minutes for the first infusion. If well tolerated, it may be administered over 30 minutes for subsequent treatments. On days when both study drugs are due to be administered, INCMGA00012 study product is administered first prior to administration of INCAGN01876. The only dose of INCAGN01876 used for this study is 300mg. There is no dose escalation or reduction. A 1-hour observation period is recommended after the INCMGA00012 infusion prior to beginning the INCAGN01876 infusion.

Preclinical assessments used to evaluate theoretical safety concerns with INCAGN01876 eliciting adverse proinflammatory infusion reactions did not induce cytokines that in vivo would be predictive of CRS in participants, so the risk of significant infusion reactions is considered to be low. For participants who have an infusion reaction associated with administration of INCAGN01876, signs and symptoms would usually develop during or shortly after drug infusion

and generally resolve completely within 24 hours of completion of infusion. Infusions reactions should be managed according to the guidelines in [Section 5.8.2](#).

5.6 Concomitant Medications:

1) Following start of study drug, concomitant medications and therapies deemed necessary for the supportive care and safety of the subject are allowed, provided their use is documented in the subject records and on the appropriate case report form. This includes corticosteroids of any dosage for the management of brain edema related to the tumor and/or study drugs. The administration of any other anticancer agents including chemotherapy and biologic agents (such as bevacizumab) is NOT permitted. Similarly, the use of other concurrent investigational drugs is not allowed.

2) List of medications that are prohibited during this study:

- Any anticancer medications, including chemotherapy or biologic therapy other than the study medications
- Any immunological-based treatment for any reason, with the exception of corticosteroids
- Any investigational agents other than INCAGN01876 and INCMGA00012
- Radiation therapy other than the SRS (8Gy x 3 fractions) administered as part of this protocol
 - Live vaccines. Examples include but are not limited to measles, mumps, rubella, varicella/zoster, yellow fever, rabies, Bacillus Celmette-Guerin (BCG), and typhoid. Intranasal influenza vaccines are not allowed.

Subjects who, in the assessment by the investigator, require the use of any of the aforementioned treatments for clinical management should be removed from the study.

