3.3. Duration of Individual Subject Study Participation

After signing the ICF, screening procedures commence. Each enrolled subject begins study treatment. Treatment continues until the subject meets any one or more of the criteria for study drug discontinuation (see [Section 5.7; Study Drug Discontinuation Criteria](#)). When a subject discontinues study drug but has not withdrawn consent, the subject enters the follow-up period. Subjects are taken off study if any of the following criteria apply:

- Lost to follow-up
- Withdrawal of consent
- Death
- Sponsor decides to terminate the study

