and described in detail in **Appendix 1** with specific application to this protocol. These recommendations include management of the toxicity itself, as well as guidance for dose interruptions/delays of the investigational agents. There are no dose reductions or dose escalations permitted for either investigational agent.

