G3: Increase of seven or more stools per day over baseline, incontinence, hospitalization indicated, severe increase in ostomy output compared with baseline, limiting self-care ADL	Should consider permanently discontinuing CTLA-4 agents and may restart PD-1, PD-L1 agents if patient can recover to G1 or less. Administer corticosteroids (initial dose of 1-2 mg/kg/d prednisone or equivalent) Consider hospitalization or outpatient facility for patients with dehydration or electrolyte imbalance If symptoms persist ≥ 3-5 days or recur after improvement, consider administering IV corticosteroid or noncorticosteroid (eg, infliximab) Consider colonoscopy in cases where patients have been on immunosuppression and may be at risk for opportunistic infections as an independent cause for diarrhea (ie, CMV colitis) and for those who are anti-TNF or corticosteroid refractory
G4: Life-threatening consequences; urgent intervention indicated	Permanently discontinue treatment Should admit patient when clinically indicated; patients managed as outpatients should be very closely monitored Administer 1-2 mg/kg/d methylprednisolone or equivalent until symptoms improve to G1, and then start taper over 4-6 weeks Consider early infliximab 5-10 mg/kg if symptoms refractory to corticosteroid within 2-3 days Consider lower GI endoscopy if symptoms are refractory despite treatment or there is concern of new infections
(continued on following page)	

Table 2. Management of GI irAEs in Patients Treated With ICPIs (continued)

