3.0 Lung Toxicities	
3.1 Pneumonitis	
Definition: Focal or diffuse inflammation of the lung parenchyma (typically identified on CT imaging) No symptomatic, pathologic, or radiographic features are pathognomonic for pneumonitis	
Diagnostic work-up Should include the following: CXR, CT, pulse oximetry For G2 or higher, may include the following infectious work-up: nasal swab, sputum culture and sensitivity, blood culture and sensitivity, urine culture and sensitivity	
Grading	Management
G1: Asymptomatic, confined to one lobe of the lung or < 25% of lung parenchyma, clinical or diagnostic observations only	Hold ICPI with radiographic evidence of pneumonitis progression May offer one repeat CT in 3-4 weeks; in patients who have had baseline testing, may offer a repeat spirometry/DLCO in 3-4 weeks May resume ICPI with radiographic evidence of improvement or resolution. If no improvement, should treat as G2 Monitor patients weekly with history and physical examination and pulse oximetry; may also offer CXR
G2: Symptomatic, involves more than one lobe of the lung or 25%-50% of lung parenchyma, medical intervention indicated, limiting instrumental ADL	Hold ICPI until resolution to G1 or less Prednisone 1-2 mg/kg/d and taper by 5-10 mg/wk over 4-6 weeks Consider bronchoscopy with BAL Consider empirical antibiotics Monitor every 3 days with history and physical examination and pulse oximetry, consider CXR; no clinical improvement after 48-72 hours of prednisone, treat as G3
G3: Severe symptoms, hospitalization required, involves all lung lobes or > 50% of lung parenchyma, limiting self-care ADL, oxygen indicated G4: Life-threatening respiratory compromise, urgent intervention indicated (intubation)	Permanently discontinue ICPI Empirical antibiotics; (methyl)prednisolone IV 1-2 mg/kg/d; no improvement after 48 hours, may add infliximab 5 mg/kg or mycophenolate mofetil IV 1 g twice a day or IVIG for 5 days or cyclophosphamide; taper corticosteroids over 4-6 weeks Pulmonary and infectious disease consults if necessary Bronchoscopy with BAL ± transbronchial biopsy Patients should be hospitalized for further management

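### Section 5.6 removes from the study subjects who need non-steroid immunological treatment, which contradicts Appendix 1 and Section 3.3 and leaves follow-up and run-in counting unclear for immune-related events outside the Section 5.7 list

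*Combined protocol and SAP*

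**What the plan says.** Section 5.6 lists as prohibited "Any immunological-based treatment for any reason, with the exception of corticosteroids" and closes by saying that subjects who, in the investigator's assessment, "require the use of any of the aforementioned treatments for clinical management should be removed from the study". The first item of the same section says that "concomitant medications and therapies deemed necessary for the supportive care and safety of the subject are allowed".

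Section 5.8.1 refers to Appendix 1 as describing the management of immune-related adverse events (irAEs) "with specific application to this protocol". For grade 3-4 pneumonitis the appendix says that treatment "may add infliximab 5 mg/kg or mycophenolate mofetil IV 1 g twice a day or IVIG for 5 days". For grade 4 colitis it says: "Consider early infliximab 5-10 mg/kg if symptoms refractory to corticosteroid within 2-3 days". The grade 3 colitis row offers infliximab as an example of a non-steroid option and also says that one "may restart PD-1, PD-L1 agents if patient can recover to G1 or less".

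Section 3.3 says: "Subjects are taken off study if any of the following criteria apply". It then gives four reasons: loss to follow-up, withdrawn consent, death and termination by the sponsor. Needing a prohibited medication is not among them. The same section sends anyone who stops study drug without withdrawing consent into follow-up. Section 3.1.3 describes entry to follow-up only for the reasons listed in Section 5.7.

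**The concern.** Removal from a study is a stronger act than stopping a drug, and the protocol draws that distinction itself: Section 5.7 notes that a subject may stop treatment yet stay in the study for progression and survival. If 5.6 is applied as written, a subject whose irAE needs a second-line immunosuppressant leaves the study because of that need. Later safety, disease-status and survival data would then stop for a reason tied to toxicity.

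A second consequence bears on a decision. The safety run-in in Section 3.1 counts only subjects who meet a 5.7 discontinuation criterion. A subject removed under 5.6 has not necessarily met one, so two readers could count the same case differently.

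**Working it through.** The plan gives no figure on this point, so the check is a comparison of passages, with simple counts for the run-in. The sample size and primary test are not affected.

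**Step 1. Does 5.6 reach the agents in Appendix 1?** The term for immunological treatment is not defined. However, the ban applies whatever the reason and exempts only corticosteroids, which implies that other immunosuppressants are covered. The allowance for supportive and safety therapy in the same section points the other way, so 5.6 is also in tension with itself.

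**Step 2. Which Appendix 1 events are already caught by a named 5.7 criterion?**

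| Appendix 1 event | Non-steroid agent | Resumption in the row | Named in 5.7 |
|---|---|---|---|
| Pneumonitis, grade 3-4 | infliximab, mycophenolate, IVIG or cyclophosphamide (optional) | no | yes |
| Hepatitis, grade 3 | mycophenolate or azathioprine (optional) | no | yes |
| Myasthenia gravis, grade 3-4 | IVIG or plasmapheresis (directed) | no | yes |
| Colitis, grade 4 | infliximab (optional) | no | yes, as a grade 4 irAE |
| Colitis, grade 3 | infliximab (optional) | PD-1 agents may restart | no |
| Inflammatory arthritis, grade 3 | synthetic or biologic DMARD (optional) | may resume | no |
| Aplastic anemia, grade 2 | ATG with cyclosporine (directed) | hold, not a permanent stop | no |

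The first four rows reach follow-up through 5.7 and 3.1.3 whatever 5.6 says. The last three meet no named criterion at onset. They would be caught only by the 5.7 items that rest on investigator judgment, or by the 5.7 rule on failure to improve, or to taper steroids, within 12 weeks of the last dose. One caution applies to the last row: the appendix uses its own scale there and labels that grade severe. If the investigator graded the event 4 under CTCAE 5.0, 5.7 would catch it.

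**Step 3. What happens to the last three rows?** Under 5.6 the subject is removed from the study. Under 3.3 none of the four off-study reasons applies. Under 3.1.3 no listed route leads into follow-up. In the colitis and arthritis rows, Appendix 1 foresees treatment resuming, which cannot be squared with removal.

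**Step 4. Effect on the run-in.** Section 3.1 continues at 0-1 of the first 3 and pauses at 2. It opens both cohorts at 0-2 of 6 and pauses at 3 or more. If one case is removed under 5.6 and not counted:

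- First stage: 2 of 3 (pause) is read as 2 - 1 = 1 of 3 (continue).
- Second stage: 3 of 6 (pause) is read as 3 - 1 = 2 of 6 (open both cohorts).

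The 12-week rule does not help in time. It needs up to 12 x 7 = 84 days from the last dose, whereas the monitoring period is SRS plus one 28-day cycle.

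**The case against.** The strongest reply is that follow-up is protected elsewhere and that 5.6 is only loosely worded. Much of this stands.

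- Section 9.2 requires each adverse event to be followed to resolution or stabilization, and serious events still ongoing at 12 weeks to be followed further. Section 8.2.2 puts every consented subject in the safety analysis. Section 6.2 ties the end of data collection to active withdrawal of consent. Section 3.1.3.3 searches public records when contact is lost.
- The protocol often writes off study where it means off treatment. Tables 8 and 9 time the end-of-treatment visit from leaving the study, while 3.1.3.1 ties the same visit to leaving study treatment. Section 5.6 may be another instance.
- Much of Appendix 1 is phrased as an option, its tables are reproduced from a published guideline, and 5.6 leaves the need for treatment to the investigator.

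A reader might therefore infer too much from 5.6. The documents do not support the claim that the worst toxicities lose follow-up: grade 4 irAEs (apart from endocrinopathy controlled by hormone replacement) and the named grade 3 irAEs are 5.7 criteria. An irAE will also normally have been recorded and graded before a second-line agent is considered, so its occurrence is not lost.

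Nor do they support the inference that 5.6 inflates PFS or OS by removing subjects who start another anticancer therapy. Section 3.1.3.2 ends disease-status follow-up at new antineoplastic therapy by design, the survival stopping list in 3.1.3.3 does not include new therapy, and where progression comes first the PFS event is already recorded.

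What the reply does not remove is the instruction itself. Loose usage elsewhere makes the milder reading plausible but does not settle it, and none of the passages cited says how a 5.6 removal counts in the run-in.

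**Conclusion.** The contradiction is real and narrow. Section 5.6 conflicts with Appendix 1 on non-steroid immunosuppression and with 3.3 on who leaves the study. For irAEs outside the 5.7 list, a literal reading ends safety, disease-status and survival follow-up and leaves their run-in status open. This rests on two assumptions: that immunosuppressants fall under the 5.6 ban, as the corticosteroid exemption suggests, and that no investigator-judgment item in 5.7 is invoked.

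The number of subjects affected cannot be given. The documents report no rate of steroid-refractory irAEs. The nearest figures, in Section 1.3.1.2, are for INCMGA00012 alone: 27 of 199 participants (27/199 = 14%) with any event of special interest, and colitis in 3 of 132 (2.3%) at 3 mg/kg every 2 weeks. These count events, not need for second-line treatment, and 5.8.1 expects that the combination could be more toxic. Any percentage of the cohort lost would be a guess. The one consequence that can be stated exactly is that a single uncounted case can reverse the run-in decision at either stage. This should be corrected, but it does not undermine the design.

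**What to change.** Reconcile 5.6 with Appendix 1, 5.7, 3.1.3 and 3.3. Which agents are permitted, and whether study drug stops or resumes, are for the sponsor to decide; no rule is proposed here.

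On data collection only:

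- In 5.6, replace removal from the study with a statement that such subjects remain in safety, disease-status and survival follow-up under 3.1.3 unless consent is withdrawn. The end points already set in 3.1.3.2 and 3.1.3.3 stay as they are.
- In 3.1.3, make clear that entry to follow-up is not confined to 5.7 reasons, so that it agrees with 3.3.
- In 3.1, state whether a subject who receives a treatment prohibited by 5.6 for an irAE counts toward the run-in rule.

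The cost is a few sentences in an amendment. The follow-up contacts are already scheduled in Table 10, so no new visits are needed.
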